5.4.2 Arm B - Usual Care

Given that we propose a cluster randomised design, some sites will be randomly allocated to receive Treatment as Usual (TAU) only. In our experience, TAU may consist of medical interventions (such as anti-androgens or anti-psychotics, though these are rarely used nowadays), nurse-delivered interventions, or counselling and risk management. Typically, the latter involves environmental adjustments (for example, being asked not to go out except with staff, being asked not to walk past schools where vulnerable children might be seen, or being asked not to attend day services with vulnerable individuals, etc). These restrictions normally form part of an individualised risk management strategy. Those in the TAU groups will not

receive any individual or group CBT interventions targeting their sexual behaviour, such as victim empathy work, cognitive distortion work, relapse prevention (sex education is permitted if need be). They may receive counselling and behavioural interventions in relation to other issues (for example anger management), and associated risk management.

We will collect data to provide a thorough description of TAU within this trial, using a proforma to record treatments received and risk management details. Additional treatments provided to men in the intervention arm will also be captured using the same form. TAU data will be collected at T2, T3 and T4 for all sites.

5.4.3 Fidelity

Sites will record location and duration of each session, therapists present at each session, participants present, participants who DNA. Fidelity will be established by video-recording treatment sessions. Where participants do not consent to video recording, we would seek to audio-record the sessions, if consent for audio-recording is not given the session will not be recorded. For each treatment site, one session will be chosen at random in each of the CBT's six modules, with experienced clinicians rating fidelity using a pre-defined rating scale (similar to that used in the anger management trail, Jahoda et al. 2013).

5.4.4 Compliance, Adherence and Acceptability

A treatment manual will be provided for all sites running the SOTSEC-ID intervention. This is lengthy (over 200 pages) and detailed. Supervision of therapists will be provided on a monthly basis and fidelity will be checked (see above). Participants' attendance at treatment sessions will be monitored.

Acceptability will be investigated by qualitative post treatment interviews with participants and therapists.

5.4.5 Concomitant Care

All patients will receive treatment as usual for their other difficulties (i.e. those not related to harmful sexual behaviours) regardless of entry into this trial. Data about concomitant care will be collected as part of the health economics evaluation, on a proforma as well as using a form to detail TAU/ additional treatments throughout the trial.

5.4.6 Protocol Treatment Discontinuation

In consenting to the trial, participants are consenting to trial treatment, trial follow-up and data collection. However, an individual participant may stop treatment early or be stopped early for any of the following reasons:

- Unacceptable adverse event, such as imprisonment
- Inter-current illness that prevents further treatment

- Any change in the participant's condition that in the clinician's opinion justifies the discontinuation of treatment such as deterioration in mental health where this is severe and debilitating
- Withdrawal of consent for treatment by the participant

As participation in the trial is entirely voluntary, the participant may choose to discontinue trial treatment at any time without penalty or loss of benefits to which they would otherwise be entitled. Although not obliged to give a reason for discontinuing their trial treatment, a reasonable effort will be made to establish this reason, whilst remaining fully respectful of the participant's rights.

Participants who discontinue protocol treatment, for any of the above reasons, should remain in the trial for the purpose of follow up and data analysis where possible.

5.5 Outcomes

Following the baseline assessment (Time 1), participants will be assessed at eight-months post-baseline (Time 2), and then again at both 12-months post-baseline (Time 3), and 24-months post-baseline (Time 4) - see flow chart.

5.5.1 Primary Outcomes

The primary outcome measure will be the score on the Questionnaire on Attitudes Consistent with Sexual Offending (QACSO, Broxholme & Lindsay, 2003; Lindsay et al 2006; Lindsay et al, 2007) at 12 months post-baseline (i.e. Time 3).

It might be thought desirable to use further harmful sexual behaviour as the primary outcome measure. However, the trial is relatively short, with only a two-year follow-up, and such behaviours are rare. It has therefore been decided that the primary outcome measure will be the QACSO, a well-validated measure of cognitive distortions for use with men who have IDD (see below for details). A recent review has reported that treatment programmes of the SOTSEC-ID type for men with IDD and HSB produce considerable change in cognitive distortions, with a large effect size (Patterson, 2018). Furthermore, a review by Hammond and Beail (2020) of the relationship between behaviour and cognitions in people with IDD has concluded that there is good evidence that, for sex offenders with IDD, cognitions and behaviour are related such that the QACSO is an appropriate measure.

The QACSO was developed by Bill Lindsay and colleagues in the early 2000s for the precise purpose of measuring cognitive distortions in men with intellectual disabilities who had engaged in harmful sexual behaviour (Broxholme & Lindsay, 2003; Lindsay et al 2006; Lindsay et al, 2007). It has been accepted since the late 1980s that non-disabled sex offenders engage in cognitive distortions, i.e. offence-supportive beliefs, and that these worsen as their offending continues. Moreover, there is ample evidence than non-offending men do not share these beliefs and it has long been argued that altering these beliefs is a central task in treatment. There is considerable evidence that treatment results in a reduction in these beliefs alongside reduced offending for men without disabilities (see review by Ward et al., 1997), as would be predicted by the cognitive behavioural model.

Similar evidence exists for men with IDD who have harmful sexual behaviour, most of this evidence being based on findings using the QACSO as the measure of cognitive distortions. The QACSO is completed directly with the men; it has over 60 items and assesses cognitive distortions across seven different offence types: rape; voyeurism; exhibitionism; dating abuse; homosexual assault; paedophilia; stalking and sexual harassment. The QACSO discriminates well between sexual offenders and non-offenders with intellectual disabilities, and the sub-scales differentiate men with different offence types (Lindsay et al 2006). It has good levels of test-retest reliability (Broxholme & Lindsay 2003) and other psychometric properties (Keeling et al, 2007) and has been very widely used in research on sexual offending in men with intellectual disabilities (Murphy et al, 2007; Langdon et al, 2007; Rose et al 2012; SOTSEC-ID 2010; Heaton & Murphy, 2013), the evidence being that the men's cognitive distortions reduce with treatment alongside their reduced offending.

5.5.2 Secondary Outcomes

Secondary outcome measures will be undertaken at baseline, 8, 12 and 24 months post baseline. Most of these measures will be completed with the men themselves, and some will be completed with their carers (see Table below). The measures are as follows:

5.5.2.1 Clinical outcome measures

QACSO score (only at 8 and 24 months post-baseline).

Sexual knowledge scores, victim empathy scores, locus of control and self-esteem at 8 months, 12 months and 24 months post baseline, using the following questionnaires:

General Sexual Knowledge Questionnaire (GSKQ): It is known that men with IDD have less sexual knowledge than men without disabilities, and previous studies have shown their knowledge increases with SOTSEC-ID treatment (SOTSEC-ID, 2010; Heaton & Murphy, 2013). Sexual knowledge will be measured on the GSK, developed by Talbot & Langdon (2006). This was designed for men with intellectual disabilities and has good internal consistency and split-half reliability. There are 63 items, covering physiology (with pictures), sexual intercourse, pregnancy, contraception, sexually transmitted diseases and sexuality. The maximum score is 110, with men with ID scoring around a mean of 45, allowing sufficient room for improvement.

Victim Empathy Scale-Adapted, (VES-A), was adapted for men with IDD from Beckett and Fisher's Victim Empathy Scale (Beckett and Fisher, 1994) for men without intellectual disabilities who had committed sexual offences (Keeling, Rose & Beech, 2007; Murphy et al, 2007). The original scale was already relatively accessible, so few changes were needed: the wording was simplified in places and a visual analogue was added to assist in the response scale. The resultant measure has 30 statements asking men how they felt and how their victim felt in various ways, in relation to the man's own offence. The responses are ratings of degree of agreement or disagreement on a four point scale. Lower scores indicated better empathy. For this adapted measure, which has been widely used for men with intellectual disabilities and harmful sexual

behaviour (Murphy et al 2007; SOTSEC-ID 2010; Heaton & Murphy, 2013; Langdon et al, 2007; Rose et al 2002), Cronbach's alpha was 0.91 (Langdon et al 2007).

Nowicki-Strickland Locus of Control Scale (Nowicki, 1976): the intervention is intended, in part, to help the men understand their own responsibility in their offending (so that they do not simply blame it on their victims). Several previous studies have employed a measure of locus of control, the validated Nowicki-Strickland Locus of Control Scale in recognition of this issue (eg Rose et al 2002; Rose et al, 2012).

Self-Esteem: for the men themselves, it is important to assist them to maintain their own self-esteem, which is often very low, at the start of treatment. At times, the intervention may threaten their self-esteem, partly because it helps them understand their responsibility for their behaviour. At other points the intervention will help them build their self-esteem, by recognizing how they are progressing towards 'good lives'. It is known that self-esteem correlates with good mental health so it is important to be sure that overall self-esteem rises with treatment, rather than falls, and for this reason a well-established measure of self-esteem adapted for people with IDD and with good psychometric properties (Dagnan & Sandhu, 1999; Keeling et al, 2007) will also be used at all time points.

Harmful Sexual Behaviour Schedule: Incidences of harmful sexual behaviour that have occurred during the 5 years prior to baseline, and then between baseline and 8 months, 8 and 12 months and 12 and 24 months will be recorded at baseline, 8, 12 and 24 month follow-up time points, respectively, using information from patient and carer report, case notes, police interviews, court appearances, and court convictions. Research assistants will report such incidents to the local clinician. Clinicians/professionals working with the participants have a responsibility and duty of care to report any safeguarding concerns or crimes, including sexual abuse, to the relevant authoritative body (local Safeguarding Board), when they are made aware of these during the trial.

5.5.2.2 Heath Economic Outcome Measures:

Client Services Receipt Inventory (CSRI): Use of health, social and CJS resources used by participants will be collected from a modified CSRI completed with participants and/or their carers; this will allow the cost of service use to be estimated. The CSRI will note if responses have been informed by reference to notes/records. Information about input from the MDT team (Q6c) at all timepoints will be collected by the Trial Managers from a delegated person in the site team. This is to protect the Research Assistants from becoming unblinded.

The EuroQol quality of life measure, EQ-5D-5L, a validated quality of life measure comprising of five questions or dimensions and a visual analogue scale will be completed to evaluate changes in quality of life.

5.5.3 Qualitative Study/Process Evaluation

A purposive sample of the men with HSB, therapists and carers (mainly carers who provide support to the participants but are not directly involved in the intervention), will be interviewed about their experiences of being in the trial, and/or of being a carer or therapist and/or the SOTSEC-ID groups, and how the experience has made an impact: these data will be analysed qualitatively using Interpretive Phenomenological Analysis (IPA) or Thematic Analysis (TA) (see below). Some interviews of men with HSB, therapists and carers may be conducted online, using web-based meeting platforms, in these instances the recording function may be used. However, generally encrypted Dictaphones or similar devices will be used for recording interviews. Where interviews are conducted online, participants who do not wish to be video recorded can switch off their cameras.

a) Men with HSB

A sample of men with HSB (and their carers, see below) will be interviewed after the intervention to gain an understanding of their experiences of participating. This part of the research is not hypothesis driven but aims to gain an 'insider's perspective' from which a theoretical framework regarding the subjective experiences of service users can be developed. The chosen analysis for this data is Interpretative Phenomenological Analysis (IPA). IPA attempts to reduce the complexity of experiential data through vigorous and systematic analysis in a transparent and plausible manner (Smith, 1996). It has a specific psychological focus and is suitable for data collected from relatively less articulate/forthcoming participants (Rose et al, 2019). A small number of participants is required: a few will be randomly sampled from each of the participating intervention groups (so that we achieve approximately N=15).

b) Therapists

At least one, randomly selected, therapist from each group (approximately N=15) will be invited to participate post-intervention in order to investigate their experiences of the groups, and their impressions of the 'climate' within the group and the impact of the group on the wider service. The focus of this evaluation is on the therapists' personal, subjective experiences and therefore IPA will again be utilised as the most appropriate qualitative analysis. Both service user and therapist interviews will be conducted according to a semi-structured interview schedule, containing questions which encourage the participants to focus on 'personal meaning' and making sense of their experiences of the therapeutic process.

c) Carers

A sample of family carers and paid carers, including the participants' key workers who work in the residential services where participants live, or care co-ordinators of the participants who have responsibility for managing the care of participants will be interviewed about caring for men with IDD and HSB (interviews will be after about 8 months in the trial)). For those in the intervention group (approximately N=15), they will also be asked to reflect on any changes they may have observed within individuals who they know have participated in the group. They will also be asked about the broader impact of changes observed in individuals such as in social relationships within residential and community settings. It seems likely that carers will not have such an in depth knowledge of the experience of the group. As a result it is suggested that thematic analysis is used to analyse the data from these interviews.

These studies of process will help identify which elements of the treatment package seem to have had a particular influence on individuals and may enable us to refine future versions of the intervention.

5.6 Participant Timeline

Time 1 in the table below is the baseline; Time 2 is eight months later; Time 3 is 12 months after baseline; Time 4 is 24 months after baseline.

Procedure	Who with?	Screen- ing	Time 1 Baseline		Time 2 Month 8	Time 3 Month 12	Time 4 Month 24
Consent	Man with IDD and carer	+		Alloc-			
WASI	Man with IDD	+		ation of sites to groups and			
ABAS	Carer	+		then Inter-			
QACSO	Man with IDD		+	vention	+	+	+
Record of harmful sexual behavior	Carer & case notes		+		+	+	+
Sexual knowledge	Man with IDD		+		+	+	+
Victim empathy (VES-A)	Man with IDD		+		+	+	+
Self esteem	Man with IDD		+		+	+	+
Locus of control	Man with IDD		+		+	+	+
Modified CSRI	Carer & case notes		+		+	+	+
EQ-5D-5L	Man with IDD		+		+	+	+

5.6.1 Participant Assessments

Participants' assessments will normally take place in their Community Team offices or in the secure unit, if they are detained there. Occasionally they may take place in the man's place of residence (but only if staff are present). They will be told they may bring a carer if they wish (family carer or paid carer). In our experience most men will wish to do this, as they are frequently anxious about

meeting new people (in this case the research assistant). Typically the men will ask the carer to stay for a bit, while they get comfortable with the setting and RA, and then the carer is usually able to wait outside in the waiting room. In some cases it may be necessary to conduct assessments using a web-based meeting platform (for example in the event of further restrictions due to Covid-19), though this would not be routinely offered. The men can have a carer present with them if they need support to access the web-based meeting and for other support.

The assessments on time 1, 2, 3, and 4 will take between 1 and 1.5 hours. Some men will want to do these without stopping. Some will want breaks. It will made clear to them that they may have breaks if they wish. It is anticipated that, if accompanied by a carer, it will be possible to complete the carer assessments (see Table above) after seeing each man, while the man, in turn, waits in the waiting room. Assessments are anticipated to take approximately an hour, although where short breaks are required, they may take longer; they will still be completed within one day where possible.

Research Assistants are expected to comply with local safeguarding procedures and risk assessments when undertaking assessments and interviews.

5.6.2 Early Stopping of Follow-up

If a participant chooses to discontinue their trial treatment, they should continue to be followed up as closely as possible to the follow-up schedule defined in the protocol, providing they are willing. They should be encouraged and facilitated not to leave the whole trial, even though they no longer engage in the trial treatment. If, however, the participant exercises the view that they no longer wish to be followed up, this view must be respected and the participant withdrawn entirely from the trial. University of Kent and NCTU should be informed of the withdrawal in writing using the appropriate HASB-IDD trial documentation. Data already collected will be kept and included in analyses according to the intention-to-treat principle for all participants who stop follow up early.

Participants who stop trial follow-up early will not be replaced.

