	behaviours which show risk of HSB, or cognitive distortions commensurate with HSB should be provided. c) Relatively good verbal comprehension (to be judged by clinicians). d) Has capacity to provide informed consent. Exclusion criteria for men: a) Major mental health difficulties that would prevent participant from taking part in group CBT b) Resident in prison or in high secure services, or on a probation order, with a sex offender treatment requirement. c) Has completed CBT for HSB in the preceding three years
	A Carer will be recruited, one for each man. They may be a family member (e.g. a parent) or a paid carer. They must know the man well. * any potential participants with an IQ => 80 need to be discussed with the CI/TMG on a case by case basis
Study Type	Cluster randomised, single-blinded, controlled trial of the effectiveness and cost effectiveness of community or secure unit delivered group CBT for harmful sexual behaviour in men with IDD with an internal pilot and embedded process evaluation.
Date of First Enrolment	1 st April 2022
Target Sample Size	240
Primary Outcome(s)	Cognitive distortions, as measured on the QACSO (Questionnaire on Attitudes Consistent with Sex Offences) measured at 12 months. This will be measured at baseline (time 1); after the intervention (time 2, eight months after baseline); and at two follow-ups (time 3, i.e. 12 months after baseline, and time 4, i.e. 24 months after baseline).
Key Secondary Outcomes	 Changes from baseline of: Further harmful sexual behaviour (from carers' report) Men's Sexual Knowledge, as measured on the General Sexual Knowledge Questionnaire (GSKQ) Men's Victim empathy (using the Victim Empathy Scale – Adapted (VES-A) Men's Self-esteem on the Rosenberg Scale Men's Locus of control, using the Nowicki-Strickland Locus of Control Scale Health care and other service use by participants, collected using a modified CSRI Men's Quality of Life, using the EQ-5D-5L

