The participants recruited for the trial will not necessarily have been convicted or even charged for sexual crimes, given the arbitrariness of police involvement for those with IDD, but there will need to be very good evidence from carers and case notes of harmful sexual behaviour. HSB will be defined as sexual behaviour in which the other person was not consenting (or was unable to consent), and the sexual behaviour would be defined as illegal (whether or not the police had been involved). Most men presenting for treatment in clinical services for this kind of behaviour have a history of more than one incident. Incidents may not have been reported by the victim (who may be someone with more severe intellectual disabilities and may have very poor or no verbal communication skills). The incidents also may not have been reported to the police by professionals or someone in the community, because they realise the person has intellectual disabilities and they may think that they are not suitable to be dealt with by the Criminal Justice System.

*A few men with IDD and HSB decide that they wish to adopt the female gender. We will not exclude these transgender individuals from the trial. For ease, though, we have continued to refer to 'men' in this protocol. That should be taken as meaning 'assigned male at birth'.

It is anticipated that some men may be in low or medium secure health services, while some may be legally unrestricted, living in the community. Groups may include some or all of these categories (as was the case in SOTSEC-ID, 2010 and in Heaton and Murphy, 2013). It is likely that all participants will also have family carers or paid carers who will be invited to take part in the research (see below for details). Men in prisons, on probation (with a sex offender treatment order) and in high secure services will be excluded. If men are imprisoned during the treatment trial (i.e. during the six months of treatment) they will discontinue in the treatment group but be included in the intention to treat analysis.

Participants with autism will **not** be excluded as long as they also have mild or borderline ID. Though they may find group treatment difficult, the evidence is that many were included in previous group CBT research (e.g. SOTSEC-ID, 2010; Heaton & Murphy, 2013) and they themselves have said they found the treatment helpful (Melvin, Langdon & Murphy, 2019).

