5.6.4 Loss to Follow-up

Where participants are lost to follow-up every effort will be made to trace their whereabouts. In our experience men with IDD and harmful sexual behaviour are very rarely lost to follow-up since they are usually on the sex offender register.

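### Section 5.6.2 withdraws a man from all data collection once he declines follow-up, with no consented option to continue carer and record-based reporting of harmful sexual behaviour

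*Protocol*

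**What the plan says.** Section 5.6.2 covers men who stop treatment. They should stay on the follow-up schedule if willing and be helped not to leave the trial. If a man does not want follow-up, "this view must be respected and the participant withdrawn entirely from the trial". What he has already contributed is protected: "Data already collected will be kept and included in analyses according to the intention-to-treat principle".

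HSB does not depend mainly on his attendance. Section 5.5.2.1 collects it "using information from patient and carer report, case notes, police interviews, court appearances, and court convictions". In the section 5.6 table, the row "Record of harmful sexual behavior" names its source as "Carer & case notes" and does not list the man. The summary in section 1.3 names carers' report alone. The modified Client Services Receipt Inventory (CSRI) has the same entry in the table as HSB.

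Section 5.11.3 states that adverse events and serious adverse events are not collected. Incidents of harmful behaviour take their place and go to the Data Monitoring Committee (DMC) as they accumulate.

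Two other sections bear on the rule. Section 6.5 tells the man that he may refuse the whole trial or any part of it, at any time. Section 6.1 says that after randomisation he has to stay in for follow-up, and then that he may change his mind about follow-up.

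**The concern.** The rule in section 5.6.2 has two end states: all scheduled follow-up, or none. A man who objects only to the interviews, put at 1 to 1.5 hours in section 5.6.1, fits neither. He can be placed only by keeping him in against his wish or by withdrawing him completely. In the second case, carer and record-based HSB reporting also stops, although it could continue with his permission and without his attendance.

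This matters more than it would for an ordinary secondary outcome. Reducing further HSB is a stated aim (section 4.2), section 5.5.1 describes such behaviour as rare, and it is the harm information that the DMC sees. Nor is the loss easily repaired afterwards. Section 5.10.4.5 makes complete cases primary, section 5.10.4.1 analyses secondary outcomes in the same way, and any imputation can draw only on what was collected.

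**Working it through.** The plan has no figure of its own on this point to reproduce. The check is a comparison of sections, followed by a bound.

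**1. Sections side by side**
- 5.6.2: declining follow-up leads to complete exit, with no partial option.
- 6.5: refusal of any single part is allowed.
- 6.1: he must remain for follow-up, yet may reconsider follow-up.
- 5.3.1 and 5.3.1.2: carer data rest on the man's consent and his nomination of the carer. Permission for this source is therefore already sought separately and could be asked about again at withdrawal.

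Section 5.6.2 does not carry through the partial choice promised in 6.5.

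**2. What is lost for one man**

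Incidents are recorded retrospectively at months 8, 12 and 24, so a man who leaves between visits also loses the window in progress:
- leaves before month 8: 24 of 24 months of post-baseline HSB unrecorded;
- leaves between months 8 and 12: 24 − 8 = 16 months unrecorded;
- leaves between months 12 and 24: 24 − 12 = 12 months unrecorded.

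**3. How many men**

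Inputs from section 5.7: target 240, attrition 20%, with experience said to be below 20%.
- Ceiling, if every loss were refusal of follow-up: 0.20 × 240 = 48 men.
- If 5% refused (an assumption): 0.05 × 240 = 12 men.

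The protocol does not divide attrition by cause, so the true number is unknown.

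**4. What it could do to the HSB rate (illustration only)**

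The protocol gives no HSB rate. Let p be the rate in men followed, w the fraction withdrawn, and R the risk in withdrawn men relative to p. The full-cohort rate is (1 − w)p + wRp. With p = 10% assumed:

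| w | R = 1 | R = 2 | R = 3 |
|---|---|---|---|
| 20% | 10% | 0.8×10% + 0.2×20% = 12% | 0.8×10% + 0.2×30% = 14% |
| 5% | 10% | 0.95×10% + 0.05×20% = 10.5% | 0.95×10% + 0.05×30% = 11% |

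If withdrawn men had half the risk (R = 0.5) and w = 20%, the full rate would be 0.8×10% + 0.2×5% = 9%, so the error can run the other way. For R above 1 these gaps are upper limits, because the formula treats withdrawn men as contributing no HSB and section 5.6.2 keeps what was recorded before they left.

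**5. Between arms**

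The full rate equals p × [1 + w(R − 1)]. If w and R are the same in both arms, the factor cancels and the risk ratio is unchanged. It moves only if they differ. For example, with R = 2 in both arms and w of 20% against 5%, the factors are 1.20 and 1.05, and 1.20/1.05 = 1.14. The protocol gives no reason to assume any particular difference.

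**The case against.** The strongest reply has four parts.

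- **The trigger is refusal of follow-up itself.** Section 5.6.2 does not mention a man who dislikes only the interviews, section 6.5 already allows partial refusal, and sections 5.6.2 and 5.10.3 both call for effort to keep collecting data. This is fair, and it means the defect may be one of wording. But the operative rule names complete exit and no intermediate step, and site staff will apply that rule.
- **The withdrawal form is not shown** and may record levels. It may. A form that did so would go further than section 5.6.2 provides, so the text would still need correcting.
- **Carer and record data need the man's permission.** This stands in full. Ending collection when he refuses everything is correct. The point is only that he is not offered the narrower choice.
- **The numbers may be small.** This also stands: section 5.7 expects attrition below 20%.

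A reader might infer more: that the harm outcome is lost outright, and for the men at highest risk. The documents do not support this. Data collected before withdrawal are retained, and nothing says that men who decline follow-up have more HSB. Section 5.4.6 lists imprisonment and deteriorating mental health as reasons to stop treatment, which the protocol keeps distinct from stopping follow-up.

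A reader might also see a contradiction in section 5.6.4, which calls these men "very rarely lost to follow-up since they are usually on the sex offender register", while section 5.3.1 says that participants "will not necessarily have been convicted or even charged for sexual crimes". The two are in tension, but usual registration and non-universal conviction can both be true. The 20% in section 5.7 is a planning allowance and does not contradict section 5.6.4 either. Deleting the register remark would change no procedure.

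**Conclusion.** The point holds as a cheap improvement to a rule that the protocol fixes explicitly. Section 5.6.2 ends all data collection for a man who declines follow-up and offers no intermediate choice, which does not match section 6.5. The avoidable loss is between 12 and 24 months of post-baseline HSB per man affected, depending on when he leaves. It applies to those men who would have accepted carer and record-based reporting.

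The number of such men is unknown. It is at most 48 of 240, and that assumes that all planned attrition is refusal of follow-up and that every such man would agree to the narrower option. The size and direction of any bias, overall or between arms, cannot be derived from the protocol. The HSB rates and relative risks used above are assumptions.

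**What to change.** In section 5.6.2, replace complete withdrawal as the single outcome with three recorded levels, each with the man's consent:

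1. stops treatment and continues all assessments;
2. stops face-to-face assessments but permits continued carer and record-based collection of HSB, and of the CSRI as far as possible, to 24 months;
3. withdraws from all further data collection.

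Offer level 2 before recording level 3, and leave the man free to choose level 3. Bring sections 5.6.2, 6.1 and 6.5 into line with these levels. Recovery of the CSRI will be partial, because section 5.10.5 prefers the man to be present at that interview.

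The cost is an amendment to the withdrawal form, the Easy Read information sheet and the consent wording, and possibly re-consent of men already enrolled. No assessment is added to the schedule, although at level 2 the carer would be contacted separately and not after the man's session.
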